5.2.11.4. Laboratory Measures – Insulin Antibodies

At each visit (baseline, visits 4, 6, 12, and 24-week (last observation carried forward [LOCF])), total insulin antibody status and its level of total percent binding will be collected. The lower limit of detection of total insulin antibodies is 1.19%. If antibodies are detected then cross reactive antibody status and its level of cross-reactive percent binding will be recorded. The lower limit of detection of cross-reactive antibodies is 1%.

Descriptive and inferential analyses will be performed for the set of FAS patients with a valid antibody testing (detected or ND) at baseline and at least one post baseline visit.

The proportion of patients with detected insulin antibodies will be summarized as counts and percentages at baseline, at each visit, at the 24-week endpoint (LOCF), and overall for the 24-week treatment period. At each of these time points, the proportion of patients with detected antibodies will be compared between treatment groups using Fisher's exact test. These analyses will be performed for patients with antibody levels detectable at baseline and for patients without detectable levels at baseline) in the FAS population.

In addition, the following listing will be provided for patients with detectable insulin antibodies at any time during the study: a listing of level of total insulin antibody percent binding across visits sorted by treatment and maximum postbaseline percent binding in descending order. Similar listings sorted by baseline percent binding as well as by endpoint percent binding will be provided. These listings will be provided for the FAS population.

The level of detectable insulin antibodies (expressed as percent binding) will be summarized by descriptive statistics (mean, median, SD, Q1, inter-quartile range (IQR), Q3, standard error, minimum, and maximum) at baseline, each visit, and endpoint (LOCF). At each of these time points, the median level of percent binding will be compared between treatment groups using the

Wilcoxon rank sum test. Graphical displays of median percent binding and IQR at each visit and endpoint (LOCF) by treatment will be presented. These analyses will be performed for the FAS population, for patients with antibody levels detectable at baseline and without detectable levels at baseline.

All of the analyses above will be performed for the level of cross-reactive antibodies as well.

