The treatment-emergent antibody response (denoted TEAR throughout this SAP) is based on the change from baseline to post-baseline in the anti-insulin antibody level (percent binding). TEAR can be sub-classified as either treatment-induced (not detected anti-insulin antibody at baseline) or treatment-boosted (detected anti-insulin antibody at baseline):

- treatment-induced response: change from not detected anti-insulin at baseline to post-baseline detected anti-insulin;
- treatment-boosted response: change from detected anti-insulin at baseline to post-baseline detected anti-insulin antibody level (percent binding) at least 147% of the baseline value.

The number and proportion of patients who have a treatment-emergent antibody response (TEAR) will be summarized by treatment at each post-baseline visit, at the 24-week endpoint (LOCF), and overall for the 24-week treatment period, then analyzed using Fisher's exact test or Pearson's chi-square test.

For patients with TEAR, a visit-wise listing of total and cross-reactive insulin antibody percent binding and clinical outcomes (HbA_{1c}, total hypoglycemia rate, basal insulin dose (U/Day, U/kg/Day) will be presented. The listing will be sorted by treatment and endpoint total insulin percent binding.

Incidence tables showing the number and percent of patients with initial and continuing TEAR at each visit will be presented. Similar analyses will be performed for the detection of total insulin antibodies and for the detection of cross reactive insulin antibodies.

Box plots of clinical outcomes (HbA_{1c}, total hypoglycemia rate, basal dose) will be generated by treatment and TEAR status.

In addition, the following patient listings of insulin antibodies (percent binding) will be provided for patients with TEAR: a listing of level of total insulin antibody percent binding across visit sorted by treatment and maximum postbaseline percent binding; a listing of level of total insulin antibody percent binding across visit sorted by treatment and endpoint percent binding. Similar listings will be presented for cross reactive percent binding.

In addition, the potential impact of total insulin antibody level and TEAR status on clinical response will be evaluated in several ways:

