1. The relationship between the natural logarithm of the last observed insulin antibody levels ($\text{Ln}[\text{antibody level}]$) and selected clinical response variables (efficacy and safety measures (eg HbA_{1c}, total hypoglycemia rate, basal dose [U/day, U/kg/day],) will be evaluated using scatterplots and analyzed using ANCOVA on efficacy/safety

measure as the dependent variable with treatment, and entry use of insulin scretagogue (SU, meglitinide, neither) as fixed effects; baseline HbA_{1c} value, baseline response variable, Ln(antibody level) and treatment-by-Ln(antibody level) interaction as covariates for the FAS patients with detectable antibodies postbaseline and with valid antibody testing at baseline (detected, ND). A significant treatment-by-insulin antibody interaction may be indicative of a differential treatment effect necessitating further exploration to determine the nature of the interaction. Only patients with non-missing baseline value and at least one non-missing post-baseline value of the clinical response variable will be included in the analysis.

2. The relationship between TEAR and selected clinical response variables (efficacy and safety measures (e.g. HbA_{1c}, total hypoglycemia rate, basal dose [U/day, U/kg/day],) will be analyzed using ANCOVA on efficacy/safety measure as the dependent variable with treatment, TEAR (yes/no), entry use of insulin scretagogue (SU, meglitinide, neither), treatment-by-TEAR interaction as fixed effects, baseline response variable and baseline HbA_{1c} value as a covariate for the FAS patients with detectable antibodies postbaseline and with valid antibody testing at baseline (detected, ND). A significant treatment-by-TEAR interaction may be indicative of a differential treatment effect necessitating further exploration to determine the nature of the interaction. Only patients with non-missing baseline value and at least one non-missing post-baseline value of the clinical response variable will be included in the analysis.

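### The SAP's TEAR model (5.2.11.4, item 2) is restricted to patients with post-baseline antibodies, so its TEAR contrast has no antibody-free comparator and is confounded with baseline antibody status

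*SAP*

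**What the plan says.** SAP 5.2.11.4 defines two forms of TEAR. The first is "treatment-induced response: change from not detected anti-insulin at baseline to post-baseline detected anti-insulin". The second, the boosted form, applies to patients detected at baseline whose later percent binding is at least 147% of the baseline value. TEAR counts "will be summarized by treatment at each post-baseline visit, at the 24-week endpoint (LOCF), and overall for the 24-week treatment period".

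The section then announces that "the potential impact of total insulin antibody level and TEAR status on clinical response will be evaluated in several ways", and lists three items:

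- **Item 1** regresses clinical response on the "natural logarithm of the last observed insulin antibody levels", in patients with detectable post-baseline antibodies.
- **Item 2** fits an ANCOVA with treatment, TEAR (yes/no), secretagogue use, treatment-by-TEAR, baseline response and baseline HbA1c. Its population, followed by the start of its rule for reading the interaction, is given as "for the FAS patients with detectable antibodies postbaseline and with valid antibody testing at baseline (detected, ND). A significant treatment-by-TEAR interaction may be indicative". It has no term for baseline antibody status and names no time window for TEAR or for detection.
- **Item 3** compares adverse event categories between TEAR and non-TEAR patients in the FAS.

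Earlier, the section sets out its antibody analyses "for the set of FAS patients with a valid antibody testing (detected or ND) at baseline and at least one post baseline visit". For detection rates it adds: "These analyses will be performed for patients with antibody levels detectable at baseline and for patients without detectable levels at baseline". Box plots of the same clinical outcomes "will be generated by treatment and TEAR status", with no restriction to detectable patients stated.

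**The concern.** A yes/no model of TEAR reads as a comparison of patients who developed or increased antibodies with patients who did not. The filter in item 2 removes most of the second group, namely everyone who never had a detectable antibody after baseline. Those left as TEAR = no are a small and different population, since they carried antibodies before the first dose.

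Item 2 is the only model in the SAP of TEAR against HbA1c, hypoglycemia rate and dose. As written it could give false reassurance (a null result because both groups carry antibodies) or a false signal (a difference that belongs to baseline antibody status). Item 1 needs the filter because its covariate is the logarithm of a measured level. Item 2 has no such covariate, and no reason for the filter is given. Items 2 and 3 also use different non-TEAR groups under the same label.

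**Working it through.** The plan states no figure for this point, so the check is first logical and then illustrative.

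**Step 1. Apply the item 2 filter to the TEAR definition (same window for detection and TEAR; ND = not detected).**

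| Baseline | Post-baseline | TEAR | In item 2 set? |
|---|---|---|---|
| ND | ND | no | no |
| ND | detected | yes (induced) | yes |
| detected | ND | no | no |
| detected | detected, <147% of baseline | no | yes |
| detected | detected, ≥147% of baseline | yes (boosted) | yes |

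The only TEAR = no row left is the non-boosted baseline-positive one.

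**Step 2. Does the unstated window matter?** There are four post-baseline antibody visits, which gives 2^4 = 16 patterns for baseline-ND patients and 3^4 = 81 for baseline-positive patients, 97 in all. Never-positive patterns in the item 2 set number 0 under all four combinations of window (detection and TEAR each at any visit or at endpoint). Baseline-ND patterns in TEAR = no number 0 under three combinations and 7 under one (detection at any visit, TEAR at endpoint). Those 7 are transiently positive patients. With detection at endpoint and TEAR at any visit, 26 TEAR patterns drop out of the set.

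**Step 3. Illustrative counts.** From the SAP: N = 530 (353/177) and SD 1.3 for HbA1c change (section 5.1). Assumed, not in the documents: proportion positive at baseline P = 2, 5, 10%; boosted among persisting positives K = 20, 35, 50%; induced among baseline-ND Q = 5, 10, 20%; 90% of baseline positives stay positive; all patients tested; detection at any visit and TEAR overall.

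| Cell | Formula | P=5%, K=35%, Q=10% | Range over 27 points |
|---|---|---|---|
| Induced | N(1−P)Q | 530×0.95×0.10 = 50.4 | 24-104 |
| Never detected | N(1−P)(1−Q) | 530×0.95×0.90 = 453.2 | 382-493 |
| Boosted | 0.9NPK | 0.9×530×0.05×0.35 = 8.3 | 2-24 |
| Non-boosted | 0.9NP(1−K) | 0.9×530×0.05×0.65 = 15.5 | 5-38 |
| Reverted to ND | 0.1NP | 0.1×530×0.05 = 2.7 | 1-5 |

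TEAR = yes is 28-119 in either set. TEAR = no is 5-38 as written (2-13 on Lantus) and 411-502 in the general antibody set.

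**Step 4. What the TEAR coefficient estimates** (no other covariates, no treatment difference):

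- *Any post-baseline antibody shifts HbA1c change by 0.30.* As written: 0.30 − 0.30 = 0.00, and still 0.00 if a baseline-status term is added inside the restricted set. In the general set with an additive baseline term: 0.210-0.295. Induced versus never-detected within baseline-ND patients: 0.30.
- *Only induced antibodies shift it by 0.30.* As written: 0.30 × induced/(induced + boosted). At the middle point this is 0.30×50.4/58.7 = 0.26; over the grid, 0.15-0.295.
- *TEAR does nothing, but baseline-positive patients differ by d.* As written: d × [boosted/(induced + boosted) − 1]. At the middle point this is (8.3/58.7 − 1)d = −0.86d; over the grid, −0.50d to −0.98d. In the general set with baseline status in the model: 0.

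**Step 5. Precision.** 95% half-width = 1.96 × 1.3 × √(1/n1 + 1/n2).

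- Induced versus never-detected, middle point: 1.96×1.3×√(1/50.4 + 1/453.2) = 0.38; range 0.28-0.54.
- Treatment-by-TEAR: 2:1 allocation multiplies each 1/n by 1.5 + 3 = 4.5. As written, middle point: 1.96×1.3×√(4.5×(1/58.7 + 1/15.5)) = 1.54; range 1.02-2.66. In baseline-ND patients of the general set: 0.80; range 0.59-1.14.

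With other assumptions (3-20% baseline-positive, 10-30% induced, 20-50% of baseline positives boosted, 20% of the remaining positives reverting), TEAR = no grows from about 6-68 to about 350-475 patients.

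**The case against.** A reader might infer that item 2 cannot detect any effect of newly developed antibodies. The documents do not support that. The 0.00 arises only if new and pre-existing antibodies act alike; if only induced antibodies act, most of the effect usually remains (0.15-0.295 of 0.30). Nor would every baseline-status difference surface as a TEAR effect. Item 2 adjusts for baseline response and baseline HbA1c, so only the residual difference would, and the d range above ignores that adjustment. Nor is TEAR = no made up solely of baseline-positive patients under every reading of the window. These limits stand and are built into the point.

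A second objection is that the only result item 2 offers to interpret is the treatment-by-TEAR interaction. With detection at any visit and TEAR overall, the TEAR = yes patients are the same people in either set. That is true, but the other half of the interaction is the treatment difference among TEAR = no patients, which as written rests on the 5-38 above.

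A third is that correction gains little. The induced contrast has a half-width below 0.30 at only 9 of the 27 grid points (those with Q = 20%), and power for a 0.30 shift is about 19-56%. The interaction half-width stays above the 0.40 margin. Agreed: the gain is mainly a contrast with a clear meaning, and only partly precision.

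Last, the box plots, item 3 and item 1 cover part of the ground, and Protocol 12.2.9.1 commits only to antibody level, so item 2 is an SAP addition. This limits the weight of the point. It does not repair item 2, which states its own narrower population and would be programmed that way.

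**Conclusion.** The point holds in this form. By the SAP's own TEAR definition, item 2 has no antibody-free comparator under any window, and its TEAR contrast is confounded with baseline antibody status. That part is logical and needs no assumed rate. All the sizes rest on assumed antibody rates, because the documents give none.

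A reader might go further and see a threat to the noninferiority conclusion or to the immunogenicity comparison between arms. Neither follows. No decision rule depends on item 2, and the primary HbA1c analysis, antibody detection and TEAR incidence by treatment, the box plots and item 3 do not use its filter. The point is worth correcting because a stated model would give a misleading contrast and the correction is cheap.

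**What to change.** In SAP 5.2.11.4, item 2:

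- Replace the population with the section's general antibody set: a valid result (detected or ND) at baseline and at at least one post-baseline visit.
- State that TEAR is overall for the 24-week treatment period and that never-detected patients count as TEAR = no.
- Add baseline antibody status (detected/ND) to the model.
- Report induced versus never-detected within baseline-ND patients as the main contrast, since an additive baseline term alone mixes it with the boosted contrast (0.210-0.295 rather than 0.30 in step 4). Report boosted patients descriptively when they are few.
- Show treatment-by-TEAR cell counts, and give estimates with confidence intervals.
- If a minimum cell size is used (section 5.2.12 gives 20 per cell as an example for subgroups), apply it equally to induced and boosted cells. On the assumed grid the induced Lantus cell is 8-35 patients and falls below 20 at 18 of 27 points; the boosted Lantus cell (1-8) is always below 20.
- Describe results as associations, because TEAR arises after randomization.

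Keep the detectable-post-baseline restriction for item 1 only. The cost is a short SAP edit, a changed population filter, a revised model and slightly more reporting; no new data are needed. The treatment-by-TEAR interaction will remain imprecise, and the report should say so.

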5.2.11.5. Vital Signs

Vital signs measures (systolic blood pressure, diastolic blood pressure, and heart rate) and their change from baseline will be summarized by descriptive statistics (mean, median, SD, standard error, minimum, and maximum) by visit for the FAS population.

In addition, the MMRM model will evaluate the change from baseline in vital sign measure as the dependent variable with treatment (LY2963016, Lantus®), entry use of insulin scretagogue (SU, meglitinide, neither), visit, and interaction between visit and treatment as fixed effects; the baseline value of the vital sign measure and the baseline HbA_{1c} value as covariates; and a random

effect for patient. The LSM means will be estimated using the observed margins (OM) option in SAS MIXED procedure.

The number and percentage of patients with treatment-emergent outlier vital sign measures during study treatment (overall) will be presented and analyzed using Fisher's exact test or Pearson's chi-square test for systolic blood pressure, diastolic blood pressure, and pulse rate according to the categories as listed below:

- low systolic blood pressure (≤ 90 mmHg and a decrease from baseline ≥ 20 mmHg)
- high systolic blood pressure (≥ 140 mmHg and an increase from baseline ≥ 20 mmHg)
- low diastolic blood pressure (≤ 50 mmHg and a decrease from baseline ≥ 10 mmHg)
- high diastolic blood pressure (≥ 90 mmHg and an increase from baseline ≥ 10 mmHg)
- low heart rate (< 50 bpm and a decrease from baseline ≥ 15 bpm)

high heart rate (> 100 bpm and an increase from baseline ≥ 15 bpm)

5.2.11.6. Other Safety Measures

Exposure:

Exposure to each treatment during the treatment period of the study will be calculated for each patient and summarized by treatment group. Exposure will be calculated as the number of days from the date of first dose of the study drug (or if this information is missing, from the date of randomization) to the date of last treatment dose. Exposure will be expressed in days, months (30 days) and years (365.25 days).

Listings of Hepatic Disorders and Abnormal Liver Enzymes:

A listing will be provided for patients with treatment emergent adverse events in the following MedDRA SMQs for Hepatic Disorders (Broad and Narrow SMQ):

Narrow	Biliary disorders	20000118
Narrow	Drug-related hepatic disorders – comprehensive	20000006

Additionally listings will be provided for all patients who meet at least one of the following liver enzyme outlier criteria for at least one visit: ALT > 3 ULN, AST > 3 ULN, total bilirubin > 2 ULN, or alkaline phosphatase > 2 ULN at any visit. These listings will include all liver enzymes at all visits.

Listings Based on Renal Function:

Listings will be provided for patients with severe reduction in GFR or kidney failure at any visit according to the following criteria:

- Severe reduction in eGFR ($15-29$ mL/min/ 1.73 m²)
- Kidney Failure (eGFR < 15 mL/min/ 1.73 m²).

These listings will include all estimated GFR (eGFR) at all visits.

5.2.12. Subgroup Analyses

The consistency of the treatment effect for the change in HbA_{1c} level will be assessed within subgroups in the FAS population if there are sufficient numbers of patients in each subgroup (e.g. 20 patients per cell). The following subgroups will be analyzed:

- Entry HbA_{1c} levels (<8.5%, ≥8.5%)
- Entry BMI (<28, ≥28)
- Entry BMI (<24, ≥24)
- Entry age (<65, ≥65)
- Gender
- Entry use of insulin secretagogues (SU, meglitinide, neither)
- Renal function, as estimated by estimated glomerular filtration rate (EGFR) using the MDRD formula (see [Appendix 2](#)). The following EGFR categories will be used:
 - Normal or increased GFR: EGFR (≥90 mL/min/1.73 m²)
 - Mild reduction in GFR: EGFR (60-89 mL/min/1.73 m²)
 - Moderate reduction in GFR: EGFR (30-59 mL/min/1.73 m²)
 - Severe reduction in GFR: EGFR (15-29 mL/min/1.73 m²)
 - Kidney failure: EGFR (<15 mL/min/1.73 m²).

The categories of severe reduction in GFR and kidney failure will be combined if there are fewer than 20 patients in either of these categories.

The change in HbA_{1c} from baseline to 24-week endpoint will be analyzed using MMRM with treatment (LY2963016, Lantus®), entry use of insulin secretagogue (SU, meglitinide, neither), visit, subgroup, subgroup-by-treatment interaction, subgroup-by-visit interaction, treatment-by-visit interaction, and treatment-by-visit-by-subgroup interaction as fixed-effects; the baseline value of HbA_{1c} as a covariate, and a random effect for patient for the FAS. If the subgroup is one of the stratification variables, then the subgroup will only be included once in the model. A significant treatment-by-subgroup interaction (p<.05) may be indicative of a differential treatment effect across levels of the subgroup, necessitating further exploration of the nature of the interaction.

For each subgroup listed above, the change in weight from baseline to 24-week will be analyzed using the same methodology as the subgroup analysis of HbA_{1c}, except baseline weight will be added as another covariate.

Additional subgroup analyses will be carried out on selected safety outcomes:

- a) total or nocturnal hypoglycemia at 24-week endpoint and for the overall 24-week period (rates and incidence)
- b) treatment-emergent antibody response (TEAR) at 24-week endpoint and for the overall 24-week period
- c) detectable insulin antibodies at 24-week endpoint and for the overall 24-week period
- d) categories of adverse events:
 - treatment-emergent adverse events (TEAEs) (overall incidence and preferred terms with >5% incidence)
 - TEAEs related to study drug (overall incidence)
 - special topic assessment of allergic events (overall incidence)
 - injection site reactions (overall incidence)
 - serious adverse events (overall incidence)

For rates and incidence of hypoglycemia (total, nocturnal) and categories of adverse events, the same set of 8 subgroups used to analyze change in HbA1c and change in weight will be analyzed.

For each categorical safety outcome and subgroup listed above, the proportion of patients with an event will be compared between treatments for the FAS. Within each subgroup, treatments will be compared using the Mantel-Haenszel test and the odds ratio and p-value from this test will be reported. The homogeneity of the odds ratios across subgroups will be assessed using the Breslow-Day test.

For the 8 subgroups listed above, the rate of total, severe or nocturnal hypoglycemia per year at the 24-week endpoint and for the overall 24-week period will be analyzed. Within each subgroup, treatments will be compared using the negative binomial (NB) model with treatment as the only factor. The NB mean for each treatment and their ratio with corresponding 95% confidence interval will be presented. Additionally, within each subgroup the rates will be compared using the Wilcoxon test. The significance of the subgroup-by-treatment interaction will be evaluated using a negative binomial model with factors treatment, subgroup and treatment-by-subgroup interaction. The negative binomial model will be implemented using the SAS PROC GENMOD with natural logarithm of exposure time (in days) as an offset variable. The above subgroup analysis will be performed and p-values will be provided if there are at least a total of 20 events in the combined treatment groups.

For TEAR at 24 weeks endpoint and overall, subgroup analyses will be performed only for entry age (>65, ≤65) and renal function. For detectable antibodies at 24 weeks endpoint and overall, we will not do subgroup analyses.

Other subgroup analyses may be performed if deemed appropriate as exploratory analyses.

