#### **12.2.9.4. Hypoglycemic Events**

The incidence, rate per 30 days and rate per year of hypoglycemic episodes (total, severe, and nocturnal as defined in Section 9.10) will be summarized by treatment at baseline, titration, maintenance, and overall study periods and at endpoint. The rate per 30 days between two visits is defined as the total number of episodes between the visits divided by the actual number of days between the visits, and then multiplied by 30 days.

The proportion of patients (with at least 1 hypoglycemic event (total, severe, nocturnal, and others) or incidence during the study will be summarized (counts and percentages) and analyzed using Fisher's exact test or the Pearson's chi-square test for the FAS population.

The rate of hypoglycemic episodes per 30 days and per year (total, severe, nocturnal, and others) will be analyzed at baseline, titration, maintenance, and overall study periods and at endpoint

using the Wilcoxon test. In addition, the hypoglycemia rates will also be analyzed using a negative binomial model for the FAS population with terms for treatment, baseline HbA1c, and entry use of insulin secretagogues (SU, meglitinide, neither). The offset variables are log of patient's treatment duration/30 and log of patient's treatment duration/365.25 for the models analyzing hypoglycemia rate per 30 days and per year, respectively.

In addition, the total number of patients with at least 1 hypoglycemic episode divided by the total extent of exposure in patient-years will be calculated for the overall study period and summarized descriptively for each treatment group for total, severe, nocturnal, documented symptomatic, and asymptomatic hypoglycemia definitions only. Listings of hypoglycemic episodes will be presented by visit for each subject.

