5.1. Determination of Sample Size

Based on the primary objective, to show noninferiority of LY2963016 to Lantus[®] at the 0.40% noninferiority margin (NIM), 450 completers in total with a ratio 2:1 (LY2963016 versus Lantus[®]) are needed at 24 weeks. This calculation assumes no treatment difference in HbA1c between LY2963016 and Lantus[®], common standard deviation (SD) of 1.3% for change from baseline in HbA1c, 0.05 two-sided significance level, and over 85% power. Assuming a 15% dropout rate at 24 weeks, the required number of randomized patients is 530 in total (353 for LY2963016 and 177 for Lantus[®]).

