Logistic regression will be used as a sensitivity analysis of the incidence of hypoglycemia. The model will have presence or absence of hypoglycemia as the dependent or response variable and treatment, baseline HbA_{1c}, and entry use of insulin scretagogue (SU, meglitinide, neither) as the independent terms in the model.

The rate of hypoglycemic episodes per year (total, severe, nocturnal, and others) will be analyzed at baseline, titration, maintenance, and overall study periods and at endpoint using the Wilcoxon test. In addition, the hypoglycemia rates will also be analyzed using a negative binomial model for the FAS population with terms for treatment, baseline HbA_{1c}, and entry use of insulin scretagogue (SU, meglitinide, neither).

In addition, the total number of patients with at least 1 hypoglycemic episode divided by the total extent of exposure in patient-years will be calculated for the overall study period and summarized descriptively for each treatment group for total, severe, nocturnal, documented symptomatic, asymptomatic hypoglycemia and probable symptomatic hypoglycemia. Individual patient listing of hypoglycemic events by visit will be presented for the FAS population.

All the above analysis will be repeated with the threshold of **Clinically significant hypoglycemia:** < 54 mg/dL (3.0 mmol/L) for hypoglycemia categories of total hypoglycemia,

nocturnal hypoglycemia, documented symptomatic hypoglycemia and asymptomatic hypoglycemia.

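### The subgroup and interaction models for hypoglycemia rate (SAP 5.2.12) omit baseline HbA1c and entry secretagogue use, which the main rate model adjusts for

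*SAP*

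**What the plan says.** **Main rate model.** SAP 5.2.11.2 says that "the hypoglycemia rates will also be analyzed using a negative binomial model for the FAS population". Besides treatment, this model adjusts for HbA1c at baseline and for secretagogue use at entry (three levels). Protocol 12.2.9.4 lists the same terms.

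**Subgroup rate models.** SAP 5.2.12 says: "Within each subgroup, treatments will be compared using the negative binomial (NB) model with treatment as the only factor". The interaction test uses treatment, subgroup and their product. Neither model has a term for baseline HbA1c or secretagogue use. Results are to be given once there are 20 events in the two arms combined.

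**HbA1c subgroup model.** The same section, for change in HbA1c, keeps secretagogue use and baseline HbA1c in the model and enters a stratification variable only once when it is itself the subgroup.

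**Randomization.** Protocol 9.3 stratifies by HbA1c (below 8.5% or not) and by entry secretagogue use.

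**Offset.** The SAP 5.2.12 models are fitted "with natural logarithm of exposure time (in days) as an offset variable", while the rate to be analyzed there is per year. SAP 5.2.11.2 names no offset. Protocol 12.2.9.4 does: "The offset variables are log of patient's treatment duration/30 and log of patient's treatment duration/365.25", for rates per 30 days and per year respectively.

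**Exposure.** SAP 5.2.11.6 says "Exposure will be calculated as the number of days from the date of first dose of the study drug", ending at the date of the last dose. It does not say whether both end days count.

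**The concern.** Hypoglycemia is a named secondary safety objective. The protocol itself treats secretagogues as a possible cause of hypoglycemia (9.1 and 9.8.1) and stratifies on their use. Stratification balances secretagogue use in the trial as a whole. It does not secure balance inside an age, sex, BMI or renal-function subgroup, where the arms may differ by chance. A treatment-only model passes that difference into the rate ratio and leaves the variation explained by the two covariates in the error.

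At stake are the width of the subgroup intervals and how readily a chance imbalance could be read as a subgroup difference. The offset and exposure wording raise a smaller question: on what scale the model means are printed, and whether a patient with a single dose has a usable exposure time.

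**Working it through.** **1. The plan's own figure.** The only sample size calculation concerns HbA1c (SAP 5.1): "0.40% noninferiority margin (NIM), 450 completers in total with a ratio 2:1", SD 1.3%, "0.05 two-sided significance level, and over 85% power". It states: "This calculation assumes no treatment difference in HbA1c". With 300 and 150 completers:

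- SE = 1.3 × √(1/300 + 1/150) = 1.3 × 0.100 = 0.130
- power = Φ(0.40/0.130 − 1.96) = Φ(1.117) = 0.868
- randomized = 450/0.85 = 529.4, rounded up to 530

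Both stated figures reproduce. The documents give no event rate, dispersion or precision target for hypoglycemia, so the size of this point has to rest on assumptions.

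**2. The three models side by side.**

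| Model | Treatment | Baseline HbA1c | Secretagogue use |
|---|---|---|---|
| Main hypoglycemia rate, SAP 5.2.11.2 | yes | yes | yes |
| HbA1c by subgroup, SAP 5.2.12 | yes | yes | yes |
| Hypoglycemia rate by subgroup and interaction, SAP 5.2.12 | yes | no | no |

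**3. Precision given up.** Two sets of simulated negative binomial data were analyzed with and without the two covariates. Both assume dispersion 1.5 and 15% early dropout.

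- Set A (400 data sets per setting): 2 events per year, secretagogue users with 2 or 3 times the rate, rate falling 15% per 1% HbA1c.
- Set B (300 per setting): about 10 events per year; 50% sulfonylurea, 10% meglitinide and 40% neither, with log-rate effects 0.5, 0.3 and 0 (ratios 1.65, 1.35 and 1); HbA1c effect −0.1 per 1%.

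Variance reduction = 1 − (SD adjusted / SD unadjusted)², where SD is the empirical SD of the log rate ratio.

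| Setting | SD unadjusted | SD adjusted | Variance reduction |
|---|---|---|---|
| A, 70/35 patients, user ratio 2 | 0.354 | 0.338 | 8.8% |
| A, 70/35, user ratio 3 | 0.359 | 0.324 | 18.5% |
| A, 180/90, user ratio 2 | 0.224 | 0.211 | 11.3% |
| A, 180/90, user ratio 3 | 0.220 | 0.198 | 19.0% |
| B, subgroup of 150, true treatment ratio 1.3 | 0.2469 | 0.2418 | 4.1% |
| B, subgroup of 150, true treatment ratio 1 | 0.2406 | 0.2372 | 2.8% |

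The range is about 4 to 19%, with one setting slightly lower. For interval width, √(1 − 0.041) = 0.979 and √(1 − 0.19) = 0.90, so intervals are about 2 to 10% narrower.

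**4. Bias.** In Set B with a true ratio of 1.30, the mean estimate was 1.31 unadjusted and 1.30 adjusted. With a true ratio of 1 both were 1.00. Averaged over trials, the omission does no visible harm.

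**5. Chance imbalance in a single trial.** Take 60% users (as in Set B), a 70/35 subgroup and simple random allocation within it. The SD of the difference in user proportion is √(0.6 × 0.4 × (1/70 + 1/35)) = 0.10. A one-SD imbalance, say 65% against 55%, moves an unadjusted rate ratio by (1 + 0.65)/(1 + 0.55) = 1.06 if users have twice the rate, and by (1 + 2 × 0.65)/(1 + 2 × 0.55) = 1.10 if three times. This is part of the lost precision in step 3, not an addition to it.

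**6. Day offset.** ln(days) = ln(days/365.25) + ln(365.25), and ln(365.25) = 5.9006, so only the intercept changes. On one simulated data set of 353/177, offsets in days, days/30 and days/365.25 all gave a rate ratio of 0.973 (95% CI 0.758 to 1.250, p = 0.832). The arm means were 0.0337 and 0.0346 per day, and 12.30 and 12.64 per year.

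**7. Exposure.** For a patient with one dose, last date minus first date is 0 and ln(0) is undefined. Counted inclusively, exposure is 1 day and ln(1) = 0. For a 24-week patient, 169 against 168 days is 1/168 = 0.6%. SAP 5.2.1 admits one-dose patients to the FAS. Protocol 7.2.2.2.1.1 gives the first dose on site, with self-injection from the next day, so such a patient is possible.

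**The case against.** The case for leaving the models alone has substance. The safety objective is answered by SAP 5.2.11.2, which keeps both covariates. The protocol's subgroup section specifies only HbA1c analyses. The hypoglycemia subgroups carry no decision rule and no multiplicity adjustment. With as few as 20 events across both arms, a three-level secretagogue term plus HbA1c may be unstable, so treatment-only is a defensible choice there. A fallback could also leave different subgroups analyzed by different models. The secretagogue and HbA1c subgroups already condition on one stratification factor each. All of this stands, and it limits the weight of the point. It does not explain why the simpler model applies to every subgroup, large ones included, when the same section adjusts for HbA1c.

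Four stronger readings are tempting, and the documents do not support them:

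- A reader might infer that the hypoglycemia analysis as a whole drops the covariates. Only the subgroup and interaction models do.
- A reader might infer that the day offset distorts the comparison. It changes no ratio, interval or p-value. It affects only the scale of the printed means, which multiplying by 365.25 restores.
- A reader might infer that the main model ignores exposure because SAP 5.2.11.2 names no offset. Uniform dropout of 10% against 20% would then shift the ratio by 0.95/0.90 = 1.056. But the protocol states the offset for this model, the SAP speaks of rates and describes no removal, and equal dropout would give no shift. This is missing detail.
- A reader might infer that exposure is zero for a one-dose patient. The SAP is silent on inclusive counting, so zero is one reading, and the documents give no count of such patients.

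**Conclusion.** The point holds for the subgroup and interaction rate models in SAP 5.2.12. They leave out baseline HbA1c and a randomization factor that the main rate model and the neighboring HbA1c subgroup model include, without a stated reason. The cost is about 4 to 19% of the variance of the log rate ratio (2.8% in the least favorable setting), together with exposure to chance imbalance inside subgroups. That range rests wholly on assumed event rates, dispersion and covariate effects, and it carries simulation error from 300 to 400 data sets per setting. No material bias was found, and nothing shows that any hypoglycemia conclusion would change. The primary result and the main hypoglycemia comparison are untouched. This is a cheap improvement. The offset and exposure points are clarifications of wording only.

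**What to change.** In SAP 5.2.12, specify the within-subgroup model as negative binomial with treatment, baseline HbA1c and entry secretagogue use, omitting the last where it defines the subgroup. For the interaction test, add subgroup and treatment-by-subgroup, entering secretagogue use once when it is the subgroup. Name treatment-only as the fallback if the adjusted model does not converge, and mark in the output which model each subgroup used.

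As accompanying clarifications:

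- In 5.2.11.2 and 5.2.12, give the offset as ln(exposure days/365.25), so that the model means are per year and match the protocol.
- In 5.2.11.6, define exposure as last dose date minus first dose date plus 1.

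The cost is a few lines of SAP text and the matching program changes. Both covariates are already in the main model, so no new data are needed. The downside is possible non-convergence in sparse subgroups, which the fallback covers.
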